10.6 OPERATIVE PROCEDURES

Surgical procedures should be in accordance with your routine practice and in accordance with the labeling. The surgeons should follow the procedures as described in the DFU for appropriate alignment of the IOL axis.

NOTE: *No additional refractive procedures are to be performed during the operative procedure or throughout the postoperative study period (e.g., LRI, OCCI, CRI, AK, PRK, LASIK or LASEK).*

NOTE: *Optiwave Refractive Analysis (ORA) can be used as a part of routine cataract surgery to improve accuracy of the correction. If ORA is used it will be documented in the Operative case report form.*

The Operative case report forms may include the following information:

INCISION TYPE AND SIZE

The incision may be clear corneal, limbal or scleral tunnel at the discretion of the investigator. Lenses should be inserted per the investigator's standard technique when using the JJSV-qualified implantation system.

CAPSULORHEXIS SIZE AND METHOD

The anterior capsulotomy should be made per the investigator's standard technique. The anterior capsulotomy method may be manual or laser-assisted.

LENS REMOVAL

Lens removal may be performed using phacoemulsification/aspiration only, or through laser-assisted fragmentation and phacoemulsification/aspiration.

OPHTHALMIC VISCO SURGICAL DEVICE (OVD)

OVD materials should be used as is customary for each investigator

IMPLANT INSTRUMENTATION USED

Lenses should be folded for implantation and inserted into the capsular bag using the JJSV-qualified implantation system. **NOTE:** *Capsular tension ring can be used per surgeon discretion.*

SURGICAL COMPLICATIONS

Should a surgical complication occur, implantation of a study lens will be at the investigator's discretion. However, in the event of capsular bag or zonular rupture, the study lens should not be implanted. Additionally, the lens is not to be implanted in the sulcus. In this case, the investigator may implant his/her choice of an alternative backup IOL.

If a subject with one qualifying eye does not receive the study lens due to a surgical complication, the subject may be discontinued from the study after resolution of the complication to ensure safety. Study-specific postoperative data from this subject will not be collected. If the subject has already received a study lens in the first eye, and the second eye does not receive a study lens, the subject's first eye will be followed per the protocol and the second eye will be followed to ensure safety, but data will not be reported for that eye. Thus, in this case, study-specific postoperative data for the first eye will be collected and study-specific postoperative data for the second eye will not be collected.

MEDICATIONS

Preoperative, operative and intraoperative medications should be used as is customary for each investigator and recorded in the source document for each subject, as appropriate. Only medications required for treatment of an SAE will be recorded on the case report forms.

TYPE OF CLOSURE

Wound closure is left to the surgeon's discretion and will be recorded on the case report form.

SURGICAL HANDLEABILITY QUESTIONNAIRE (SHQ)

The surgeon will complete a single-item questionnaire at the operative visit for each implanted eye. The single-item questionnaire will assess surgeon feedback on the handleability of the study lens.

Additional operative information collected may include:

- Date of surgery
- Operative eye
- Lens power and serial number
- Intended spherical equivalent
- Intended cylinder
- Capsular bag polishing
- Lens placement
- Other surgical procedures

- Difficulty of lens implantation
- Serious and/or device-related adverse events
- JJSV product complaints

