8. STUDY POPULATION

All study subjects will be enrolled from the normal surgical cataract population at up to 50 sites in the United States. Up to 1100 subjects will be enrolled in the study to achieve 1000 evaluable subjects at 3 months. However, data will be collected only for eyes implanted with the study lens. This study will include only subjects undergoing primary cataract extraction and IOL implantation and who meet all the study enrollment criteria. All subjects who meet the criteria will be offered enrollment in the study. Enrollment criteria may not be waived by the investigator. Any questions regarding patient eligibility are to be discussed with JJSV prior to subject enrollment. Subjects will be enrolled at each site sequentially until the recruitment goals are met. Enrollment will be competitive across sites.

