10.9 UNSCHEDULED VISITS

During the study period, if a non-protocol-required visit is done for the purpose of medically-indicated follow-up for either study eye, data from this visit should be submitted using the Unscheduled Visit CRF. The need for unscheduled visits is at the investigator's discretion. Specific examinations to be performed at unscheduled visits are also at the discretion of the investigator (based on the reason for the unscheduled visit), and data are to be recorded in the appropriate section of the case report form.

Data to be collected may include:

- Monocular UCDVA
- Manifest Refraction and monocular BCDVA
- Intraocular pressure
- Medical and/or lens findings, complications
- Serious and/or Device-Related Adverse events
- Ocular Medications

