11. ADVERSE EVENTS AND PRODUCT COMPLAINTS

11.1 ADVERSE EVENT DEFINITIONS

Adverse Event (AE)

An adverse event is defined (following ISO 14155) as any untoward medical occurrence, unintended disease or injury, or untoward clinical signs (including abnormal laboratory findings) in subjects, users or other persons, whether or not related to the study device.

Serious Adverse Event (SAE)

An adverse event is considered serious (following ISO 14155) if it is an untoward occurrence which may or may not be related to use of the study device that

- Is sight- or life-threatening,
- Results in death,
- Requires inpatient hospitalization or prolongation of hospitalization (a planned hospitalization for a pre-existing condition without a serious deterioration in health is not considered a serious adverse event),
- Results in permanent impairment of a body structure or body function,
- Necessitates medical or surgical intervention to prevent permanent impairment to a body structure or function, or,
- Results in fetal distress, fetal death or a congenital abnormality or birth defect

Device-Related Adverse Event/Adverse Device Effect (ADE)

A device-related adverse event is defined as any adverse event that is believed to be definitely, probably or possibly related to the study device (following the guidelines in Section 11.4, Causal Relationship). A device-related event is also considered an adverse device effect (ADE; following ISO 14155) resulting from the use of the study device that may result from user error, insufficiencies or inadequacies in the instructions for use, deployment, implantation, installation, operation or any malfunction of the device.

Study-Specific Serious Anticipated Adverse Events

The following is a list including, but not limited to, ocular serious adverse events that are anticipated and must be reported to JJSV for this study. Any events that are unlikely but anticipated (i.e., endophthalmitis or toxic anterior segment syndrome) will be reported to FDA and other appropriate regulatory agencies.

- Endophthalmitis/Intraocular infection
- Hypopyon
- Hyphema
- IOL dislocation

- Cystoid macular edema: Macular edema diagnosed by clinical examination and adjunct testing (e.g. OCT, FA) resulting in BCDVA of 20/40 or worse at 1 month or later
- Pupillary block
- Retinal detachment/tear
- Corneal edema
- Chronic iritis or uveitis
- Raised IOP that persists (i.e., is present at the last study visit)
- Toxic anterior segment syndrome (TASS)

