11.3 ADVERSE EVENT AND COMPLAINT REPORTING REQUIREMENTS

All adverse events and any complaint encountered using any JJSV product, regardless of severity and whether or not attributed to the study device(s), are to be reported to JJSV and recorded on the case report form corresponding to the visit during which awareness of the event occurred. Adverse events are also to be reported to the reviewing IRB as per their reporting requirements. If required, adverse events will be reported to the appropriate regulatory agencies (e.g., FDA) according to all applicable laws and regulations. Specific instructions on notification procedures to JJSV are included in Error! Reference source not found..

General guidelines are provided below:

Adverse Event Reporting

An adverse event that is not serious or device-related is to be reported to JJSV in a timely manner. Notification of non-serious and non-device-related adverse events will occur by submitting events on the CRF when noted. Such adverse events are also to be reported to the reviewing IRB per their reporting requirements.

Complaints/Device Deficiency Reporting

A general product complaint or device deficiency is to be reported to JJSV in a timely manner. Notification of complaints/device deficiencies will occur by either submitting complaints on the CRF when the complaint occurred (e.g., operative form) or by a phone call to the Sponsor. Any device deficiency that could have led to a serious adverse event without suitable action or intervention, or under less fortunate circumstances, must be reported to the sponsor immediately (no later than 24 hours after detection). Device deficiencies that could have led to a serious adverse event should also be reported to the investigator's IRB per their reporting requirements.

Serious and/or Device-Related Adverse Event Reporting

Serious and/or device-related events (ADEs) are to be documented using the SAE/ADE Detailed Page. In the event of a serious adverse event (SAE), which may or may not be related to use of the study device, JJSV must be notified immediately (no later than 48 hours after detection). Any SAE is to be reported by phone (and/or email) and by submitting a completed SAE/ADE Detailed Page. Any SAE or device-related AE should also be reported to the investigator's IRB per their reporting requirements.

Unanticipated Adverse Device Effect (UADE)/Unanticipated Serious Adverse Device Effect (USADE) Reporting

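### Section 10.6 bars reporting of data for a second eye that does not receive the study lens, which conflicts with Section 11.3, so a site could omit postoperative adverse events in that eye

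*Combined protocol and SAP*

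**What the plan says.** Section 10.6 deals with a bilateral case in which the first eye already has a study lens and the second does not get one. The first eye continues per protocol. As for the other, "the second eye will be followed to ensure safety, but data will not be reported for that eye". The sentence after that draws the consequence that "study-specific postoperative data for the second eye will not be collected".

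Section 8 sets a general rule in the same direction: "data will be collected only for eyes implanted with the study lens".

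The safety sections are written by subject. Section 11.1 defines an adverse event as an untoward occurrence in subjects, users or others, related to the device or not. It also lists "ocular serious adverse events that are anticipated and must be reported to JJSV for this study". Section 11.3 says that adverse events and complaints about JJSV products, "regardless of severity and whether or not attributed to the study device(s), are to be reported to JJSV and recorded on the case report form". Serious events, related or not, must reach the sponsor within 48 hours.

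On forms, Section 10.9 speaks of "medically-indicated follow-up for either study eye, data from this visit should be submitted using the Unscheduled Visit CRF". Section 11.5 asks for an Unscheduled Visit form whenever the subject returns for follow-up of a serious or device-related event, and does not restrict this by eye.

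**The concern.** The clause in 10.6 withdraws reporting for an eye in the same breath as it says the eye is being followed for safety. It carries no exception for adverse events. A coordinator could fairly read it as a specific exception to the general rule in 11.3.

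The eyes concerned are not a random sample. Section 10.6 says that the study lens should not be implanted after capsular bag or zonular rupture, so complicated operations are steered into this group. Section 11.4 counts the procedure specific to the initial application of the device as part of its use. An event that follows an attempted insertion can therefore be device-related even though no study lens stays in the eye. Section 11.1 lists retinal detachment or tear, intraocular infection, and retained lens material leading to further surgery as reportable serious events.

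What is at stake is whether such events, when they appear after surgery, reach the sponsor and the medical monitor. Section 15.3 has the medical monitor review what is reported, and the risk management text in Section 17 relies on events being reported under Section 11.

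**Working it through.** The point turns on the text, and the plan gives no figure for it. The passages are set side by side.

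1. **Is the person still a subject?** Yes. Section 10.8 says that anyone who has received at least one study lens is followed according to the protocol.
2. **Does an event in the second eye meet the definition of an adverse event?** Yes. The definition in Section 11.1 is by subject and does not depend on which eye holds a study lens.
3. **Does Section 11.3 exempt that eye?** No. It has no exclusion by eye, and it applies whatever the severity or attribution.
4. **Does Section 10.6 exempt adverse events?** No. Its first clause is unqualified.
5. **Does the following sentence in 10.6 settle the matter?** Not clearly. It refers to study-specific postoperative data, a term the protocol does not define. Section 10.7 lists medical and lens findings, complications, and serious or device-related adverse events as content of the postoperative case report form, so the term can be read to include them.
6. **Is anything from that eye captured elsewhere?** Possibly, at surgery. The additional operative information in Section 10.6 may include serious or device-related adverse events, JJSV product complaints and difficulty of implantation. The gap is therefore mainly postoperative.
7. **Does it touch the primary analysis?** No. Section 20.1 analyses only eyes implanted with a ZCU lens that have 3-month data. The precision figure in Section 20.4 also stands: 1.96 × √(0.95 × 0.05 / 1000) = 0.0135, or 1.35%, against the stated 1.4%.
8. **Can the loss be sized?** No. The synopsis plans 1,000 treated subjects, treated in one or both eyes, so operated second eyes could number anywhere from 0 (all unilateral) to 1,000 (all bilateral). The documents give no rate at which a second eye fails to receive the lens, and no event rate in such eyes.

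**The case against.** The best defence is that the two rules can be reconciled. The second sentence in 10.6 restates the exclusion as study-specific postoperative data. On that reading, study measurements stop and safety reporting continues. The duty to report is repeated elsewhere by subject: in the investigator obligations (Section 9.2), in the adverse event paragraph of Section 10.7, in Section 11.5 and in Appendix B. Section 15.2 has monitors check subject files for unreported events. Much of this stands. It shows that the plan, read as a whole, does not direct a site to withhold serious events. It does not remove the ambiguity, because no passage says that Section 11.3 prevails over the unqualified clause in 10.6.

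A reader might also infer that Sections 8 and 10.9 forbid reporting. They do not. Section 8 describes the study population and does not mention adverse events. Section 10.9 says when to use one form and prohibits nothing. The initial route for a serious event is phone or email plus the SAE/ADE Detailed Page, and Section 11.5 already covers follow-up visits by subject. These two passages need only be brought into line.

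Nor do the documents support the inference that nothing at all is recorded for such an eye, given the operative items noted above.

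**Conclusion.** The conflict is real and limited. Section 10.6 as worded leaves a site able to conclude that postoperative adverse events need not be reported for the second eye of an active subject, while Sections 11.1 and 11.3 require the report. The conclusion rests on the wording alone and on no assumed rate.

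Its size cannot be stated. A reader might be tempted to estimate the share of serious ocular events lost by assuming rates of aborted implantation and of subsequent events. The documents supply neither rate. Such a sum would have to assume complete non-reporting in spite of Section 11.3, and it would mislead if it counted all aborted implants and not second eyes only.

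The point also does not extend to a subject whose only qualifying eye fails to receive the lens. Section 10.8 makes that person a screen failure, and Section 10.6 allows discontinuation once the complication has resolved, so there may be no later study visit through which to report.

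The change should be made. It protects safety reporting, and no efficacy result depends on it.

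**What to change.** In Section 10.6, replace the clause that bars reporting for the second eye with wording such as: *effectiveness and questionnaire data will not be collected for that eye; adverse events, complaints and device deficiencies in that eye will still be reported under Section 11.3 and Appendix B.* The sentence that follows can then stay, because the scope of the exclusion has been stated.

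Two alignments go with it. In Section 8, add *except adverse events and complaints* to the sentence limiting data to implanted eyes. In Section 10.9, bring the reference to either study eye into line with the subject-level wording of Section 11.5. Leave the handling of the one-eye subject as Sections 10.6 and 10.8 have it.

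The cost is a wording amendment, a few more SAE/ADE pages and a slightly less favourable event listing. The eye is already being followed and the forms exist. Endpoints, sample size and treatment do not change.

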8. Concurrent participation or participation within 30 days prior to the preoperative visit in any other clinical study.

NOTE: *Physicians considering enrolling a patient with one or more of the conditions listed under the warning or precaution in the final approved labeling of the device should weigh the potential risk/benefit ratio before enrollment.*

DATA ANALYSIS:

For questionnaire data, the frequency and proportion with each rating for each item will be reported. For the primary endpoint, these results will also be reported by IOL model for lower-cylinder (ZCU150), medium-cylinder (ZCU225 to ZCU375) and extended higher-cylinder (ZCU450, ZCU525 and ZCU600) IOLs.

For visual acuity and refractive data, descriptive statistics will include the mean, standard deviation, median, minimum, maximum and 95% confidence intervals. For visual acuity, the frequency and proportion of eyes achieving each acuity line will also be reported. The frequency and proportion of eyes within 0.5 D and within 1.0 D of intended values will also be determined for postoperative refractive cylinder and spherical equivalent.

In addition, the frequency and proportion of eyes with medical findings, lens findings, complications and adverse events will also be reported.

STUDY VISITS AND PROCEDURES:

Subject qualifications will be assessed at the preoperative visit according to the enrollment criteria. The ICD must be signed by any patients who agree to participate in the study prior to

undergoing any study-specific procedures. This will include designation as to whether one or both eyes are to be included in the study.

Preoperative Procedures: Following informed consent, demographic, and general preoperative information will be collected from routine cataract evaluation examinations.

Operative Procedures: General operative information and responses from the Surgical Handleability Questionnaire (SHQ) will be collected for each implanted eye.

Postoperative Procedures: At the 1-week visit, uncorrected distance visual acuity (UCDVA), medical findings/complications and surgeon satisfaction with rotational lens stability will be collected. At the subject's last study visit (3-month visit), UCDVA, manifest refraction, BCDVA, keratometry, and surgeon feedback from the Surgeon Satisfaction Questionnaire (SSQ) will be collected.

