10.8 EXIT OF SUBJECTS

An Exit Case Report Form will be completed for all subjects, either when they complete the study or if they exit early.

It is the responsibility of the investigator to provide complete follow-up data to JJSV for each subject, and every attempt should be made to gather that complete follow-up data for all subjects enrolled as missing data can have a negative effect on the study results. Patients who would be traveling, relocating or otherwise unavailable for postoperative follow-up visits should not be chosen for this clinical study.

Subjects will be discontinued from the study if the study lens is removed and the fellow eye does not have a study IOL or if the subject dies. Subjects will be considered "lost-to-follow-up" from the study only if irretrievably lost for unavoidable reasons such as: subject moved/unable to locate, subject uncooperative/refuses further study participation, subject ill/unable to travel.

A subject will be considered a screen failure if he/she does not meet the enrollment criteria. A subject will also be considered a screen failure if he/she does not undergo surgery or receive a study lens for various reasons including: the planned implant being aborted due to surgical complications, the subject withdrawing consent prior to treatment or the subject died prior to

treatment. If a subject receives at least one study lens, he/she is to be followed according to the protocol.

If a subject is exited early from the study, the investigator will submit an Exit Case Report Form to JJSV indicating the reason for study exit. In the event of a lens removal or other serious adverse event, the subject may be exited from the study; however, efforts must be made by the investigator to follow the subject until resolution of the adverse event.

All study subjects are to be instructed to undergo regular eye examinations at least yearly and to return to their doctor if any eye complications are experienced in the interim.

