20.1 ANALYSIS POPULATION

For the primary endpoint, the primary analysis population will be all eyes implanted with a toric IOL (model ZCU150 through ZCU600) and with available data at the 3-month visit. For other endpoints, all eyes implanted with a toric IOL model ZCU150 to ZCU600 and with available data at the key timepoint for that endpoint will be used. In addition, data for the primary endpoint will also be evaluated by IOL model for lower-cylinder IOLs (ZCU150), medium-cylinder IOLs (ZCU225 to ZCU375) and for extended higher-cylinder IOLs (ZCU450, ZCU525 and ZCU600). For the surgeon preference questionnaire (SPQ) and the surgeon experience questionnaire (SEQ), the analysis population will be surgeons responding to these questionnaires.

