APPENDIX A: SUMMARY OF PROCEDURES REQUIRED AT EACH VISIT

Examination	Preop (Visit 1)	Op (Visit 2)	1-week (Visit 3)	3-month (Visit 4)
Informed consent, ocular history, enrollment criteria, IOL power calculations	+			
Biometry	+			
Keratometry	+			+
Lens power/serial number		+		
Surgeon Preference Questionnaire (SPQ)	+ ^a			
Surgical Handleability Questionnaire (SHQ)		+ ^b		
UCDVA	+		+	+
Manifest refraction	+			+
BCDVA	+			+
Medical findings/lens findings/complications/adverse events	+		+	+
Surgeon satisfaction with rotational lens stability (Single-item from SSQ)			+	
Surgeon Satisfaction Questionnaire (SSQ)				+
Surgeon Experience Questionnaire (SEQ)				+ ^c

^a At study start (prior to first subject implantation)^b At the operative visit for each implanted eye^c At the last subject's 3-month visit for each surgeon at each study site

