ATTACHMENT B- SURGICAL HANDLEABILITY QUESTIONNAIRE (SHQ)**Instructions**

- This questionnaire is self-administered and should be completed by the surgeon following the completion of the surgery for each eye.
- The purpose of this questionnaire is to collect surgeon feedback on the handleability of the TECNIS® Toric II IOL (study lens).

Rate your level of confidence in controlling the position of the study lens in the implanted eye?

5- Extremely confident	
4- Quite a bit confident	
3- Somewhat confident	
2- A little confident	
1- Not at all confident	

If you answered “1-Not at all confident” or “2- A little confident”, please specify reason.

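### The handleability questionnaire leaves out eyes in which insertion of the study lens was attempted but no study lens remained, which may bias the result slightly in the lens's favour

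*Combined protocol and SAP*

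**What the plan says.** Collection is tied to implanted eyes in four places:

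- Synopsis, operative procedures: "responses from the Surgical Handleability Questionnaire (SHQ) will be collected for each implanted eye".
- Section 10.1 (Overview), which says the same of the operative visit.
- Section 10.6: "The surgeon will complete a single-item questionnaire at the operative visit for each implanted eye".
- Appendix A, footnote b: "At the operative visit for each implanted eye".

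The item in Attachment B presupposes a lens in place: "Rate your level of confidence in controlling the position of the study lens in the implanted eye". The instruction above it is wider, saying that the form "should be completed by the surgeon following the completion of the surgery for each eye".

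Section 20.1 sets the analysis population: "For other endpoints, all eyes implanted with a toric IOL model ZCU150 to ZCU600 and with available data at the key timepoint for that endpoint". Section 8 adds a general rule that "data will be collected only for eyes implanted with the study lens".

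Section 10.8 makes a subject who receives no study lens a screen failure, and its listed reasons include "the planned implant being aborted due to surgical complications". Section 10.6 deals separately with a second eye that gets no study lens when the first eye has one: that eye is followed for safety but its data are not reported.

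Section 20.3 plans a frequency table for the SHQ item. It gives no success threshold, test or SHQ-specific confidence interval.

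**The concern.** Section 6 names handleability as one of three perspectives from which the lens is to be evaluated. The SHQ item asks how confident the surgeon was in controlling the lens's position. An insertion that was started and given up is a case where that confidence could well have been low. Whether an eye is rated is settled during the same operation that the rating describes. Section 10.6 leaves implantation after a surgical complication to the investigator's discretion, so the person giving the rating can also influence which eyes are rated.

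If abandoned attempts occur and would score lower than completed ones, leaving them out can only move the distribution in the lens's favour. Nothing in the plan asks for a handleability score for these eyes, or for a count of them, so a reader of the results could not tell whether the omission mattered.

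The difference between the form's instruction and the rest of the protocol adds a practical problem. Two sites could treat the same aborted case differently, and section 20.1 would then drop any rating that was obtained.

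**Working it through.** **Step 1. The plan's own figure.** Section 20.4 gives precision only for the primary endpoint: 1000 eyes, an expected 95%, and a two-sided 95% interval within 1.4%. The Wald half-width is 1.96 × √(0.95 × 0.05 / 1000) = 0.0135, or 1.35 points, so the figure reproduces. It says nothing about the SHQ and serves below only as a yardstick.

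**Step 2. Who is rated.**

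| Eye | SHQ under the plan |
|---|---|
| Study lens implanted at the first attempt | Collected and analysed |
| First study lens abandoned, a second study lens implanted | Collected and analysed (the eye is implanted) |
| Insertion attempted, no study lens remains | Not collected under 10.6; outside the 20.1 population in any case |
| Surgery complicated before any insertion attempt | Not collected; the question does not apply |

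Only the third row is at issue.

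**Step 3. Effect on low ratings.** The documents give neither an abandonment rate nor an expected SHQ result, so all inputs here are assumptions: 1000 implanted eyes, 20 of them (2.0%) rated 1 or 2, and k further eyes with an abandoned attempt, all rated 1 or 2. The share among attempted eyes is (20 + k) / (1000 + k).

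| k | Share rated 1 or 2 | Shift from 2.0% |
|---|---|---|
| 0 | 20/1000 = 2.00% | 0 |
| 5 | 25/1005 = 2.49% | 0.49 points |
| 10 | 30/1010 = 2.97% | 0.97 points |
| 20 | 40/1020 = 3.92% | 1.92 points |

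**Step 4. The same check on favourable ratings.** Let f be the share of attempted eyes that are abandoned, p the favourable share among implanted eyes and q the favourable share among abandoned ones. The all-attempted share is p(1 − f) + qf, so the drop is f(p − q). Take p = 95% (an assumption; the documents use this value only for the primary endpoint).

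| f | Drop if q = 0 | Drop if q = 0.5 |
|---|---|---|
| 0 | 0 | 0 |
| 0.1% | 0.10 points | 0.04 points |
| 0.5% | 0.48 points | 0.22 points |
| 1% | 0.95 points | 0.45 points |
| 2% | 1.90 points | 0.90 points |

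Even with q = 0, the drop reaches 1.4 points only at f = 0.014 / 0.95 = 1.47%. That is 0.0147 / (1 − 0.0147) × 1000, or about 15 abandoned eyes per 1000 implanted.

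**The case against.** The strongest reply is that no bias has been shown. It needs abandoned insertions to occur and to be rated lower, and the documents give no rate for the first and no evidence for the second. The events for which section 10.6 says the study lens should not be implanted are capsular bag or zonular rupture. These can precede any handling of the lens and need not reflect how it handles. This stands: the size is unknown and may be zero.

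A reader might infer more than the documents support:

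- *Failed attempts are never rated.* Not so where a second study lens is then implanted.
- *These eyes yield no data at all.* Section 11.3 makes all adverse events and any complaint with a sponsor product reportable. Section 10.6 allows difficulty of implantation to be recorded. Section 10.8 requires an exit form for all subjects. Section 20.3 summarises accountability and operative complications. Section 8 and the second-eye rule leave unclear how far these cover eyes without a study lens. None of them supplies a handleability score.
- *All such eyes are screen failures.* The rule in 10.8 does not cover a second eye when the first has a study lens.
- *Low ratings are understated by 20% to 49%.* That is the relative form of step 3 (1 − 2.00/2.49 and 1 − 2.00/3.92). It rests on an assumed base of 2.0% and leaves out values of k below 5. The plan also defines no 1-or-2 cut.

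It is also fair to say that the form's instruction already points to each operated eye. That makes collection ambiguous, but the item wording and the 20.1 population still exclude the eyes in question.

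**Conclusion.** The point holds in a limited form. By stated rule, in both collection and analysis, the SHQ describes only eyes that received a study lens. An eye with an attempted insertion and no study lens remaining drops out on a criterion tied to what is being rated. If such eyes exist and would score lower, the direction of bias is in the lens's favour.

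The size cannot be found from the documents and is probably small. The upper case of about 0.5 to 1.9 points assumes both that 5 to 20 such eyes occur per 1000 implanted and that every one is rated 1 or 2. A reader might conclude that the handleability result is too favourable. The documents support only that it can be, and that the plan as written could not show otherwise.

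The SHQ is a descriptive other endpoint with no threshold, and the primary endpoint is not affected. The conflict between the form's instruction and sections 10.1 and 10.6, the synopsis and Appendix A needs reconciling whatever the size of the bias.

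**What to change.** - **Collection.** In the synopsis, section 10.1, section 10.6 and Appendix A footnote b, require the SHQ for each eye in which insertion of a study lens was attempted, whether or not the lens remained. Define when an attempt starts, for example when the lens enters the eye. Eyes with a complication before that point then stay out.
- **Form.** In Attachment B, make the item refer to the operative eye instead of the implanted one, and align the instruction with the new rule.
- **Exceptions.** Add a matching exception to the data-collection rule in section 8 and to the second-eye rule in section 10.6, so that the change creates no new contradiction.
- **Analysis.** In 20.1 and 20.3, report the SHQ for attempted eyes, with the implanted-only distribution as a supporting table. Report the number of attempted-but-not-implanted eyes with reasons. If that number is zero, the report can say so and the question is closed.

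The cost is protocol and form wording plus one single-item form for a few more eyes. The downside for the sponsor is a distribution that may be slightly less favourable.
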